FluSAFE: Flu SMS Alerts to Freeze Exposure

ClinicalTrials.gov ID: **NCT03274310**

Document date: May 4, 2020

SPECIFIC AIMS

We propose to conduct a randomized controlled trial assess whether a scalable, text message-based educational intervention triggered by text message-based surveillance for influenza-like illness (ILI) in households with one or more children can decrease laboratory-confirmed influenza transmission.

Influenza infection results in an estimated 31 million outpatient visits, 55,000 to 974,200 hospitalizations (2014-15 estimate: 974,206), and 3000 to 49,000 deaths (2014-15 estimate: 49,006) annually.¹⁻³ Membership in a household in which someone else has influenza is the major risk factor for contracting influenza.⁴⁻⁷ The household secondary attack rate (SAR) is as high as 19% based on laboratory-confirmed influenza and 30% based on symptoms.⁶⁻¹⁴ Non-pharmaceutical preventive measures including education have been found to decrease influenza transmission.¹⁵ For example, in one study during the 2009 influenza A H1N1 pandemic, having had a household discussion about preventing transmission was significantly associated with decreased SAR.⁷ Most transmission occurs early in an illness,^{7,10,13} and it has been demonstrated that non-pharmaceutical interventions are effective only if started within 36 hours of index case symptom onset.^{16,17} Yet, most interventions are delayed because they are not initiated until care is sought.^{16,17} In one study, less than 30% of households were identified within 36 hours when an index case was diagnosed at a medical visit.¹⁶ We reasoned that use of home surveillance with text-message symptom reporting to trigger an educational intervention has the potential to overcome delays in implementing preventative behaviors.

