Household Transmission of Influenza. Membership in a household in which someone else has influenza is the major risk factor for contracting influenza.⁴⁻⁷ The secondary attack rate of influenza in a household is as high as 19% based on laboratory-confirmed seasonal and pandemic influenza, and as high as 30% based on symptoms for ILI/ARI.⁶⁻¹⁴ Non-pharmaceutical preventive measures including education have been found to reduce household transmission.¹⁵ One study conducted during the 2009 H1N1 pandemic found that having had a household discussion about how to prevent transmission was the only household-level factor significantly associated with decreased secondary attack rates.⁷ However, since most transmission occurs in the first few days of illness,^{7,10,13} it is important that the intervention occur as soon as possible after onset of symptoms in the index case. Cowling *et al.* demonstrated an effect of non-pharmaceutical intervention (hand hygiene alone and hand hygiene plus face mask) only when initiated within 36 hours of symptom onset in the index case.¹⁶ Seuss *et al.* also found an impact of mask or mask plus hand hygiene only in households for which the intervention was also started within 36 hours.¹⁷ Interventions will be delayed when they depend on the index case seeking care.^{16,17} In Cowling's study, less than 30% of households were identified within 36 hours of onset based on identifying index cases at a medical visit. During the 2009 H1N1 influenza A pandemic, surveillance based on medical visits for ILI was not completely useful for detecting or monitoring the outbreak due in part to the lack of timeliness of visits.²⁸ These failures to capture cases within 36 hours arise from two factors: time between onset of ILI and seeing a medical provider, and cases that are not medically attended at all. We reported that less than one-third of persons with laboratory-confirmed influenza in a community surveillance study sought medical care.¹⁸ Influenza cases have the potential to transmit infection to household members during the first 36 hours of symptoms; the earlier in this period and the higher the proportion with ILI who receive an educational intervention, the greater the potential to reduce transmission.

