2. ARI/ILI SURVEILLANCE IN A COMMUNITY-BASED SAMPLE AND TEXT MESSAGING SURVEILLANCE

2.1 MoSAIC: MOBILE SURVEILLANCE FOR ARI/ILI IN THE COMMUNITY:¹⁸ Drs. [name], [name], and [name] have used text messaging to conduct surveillance for ARI/ILI. During the first three years of the study, 62,650 text messages were sent to households; responses were received for 48,308 (77.1%). The response rate has not decreased over time. The majority (88.9%) of households who responded did so within 4 hours of messages being sent; 96.2% responded within 12 hours. The median time from symptom onset to research-assistant obtained nasal swab is 2 days; 75-80% of specimens were collected within the optimal 48-72 hour window.¹⁸

2.2 APPROPRIATE CARE OF URI IN CHILDREN OF LATINO IMMIGRANTS: THE ACURI PROJECT:⁵⁴ Drs. [name] and [name] conducted illness surveillance in household using weekly telephone reporting. There were 1,829 illnesses reported. Research staff conducted home visits on a random sample of participants with telephone reports of medication use and the telephone reports were 93.7% accurate (95% CI 86.9%-97.4%).

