Annual home visits will be made to all enrolled households wanting to continue the next respiratory season to facilitate retention and participation, answer questions, ensure contact information remains correct, update household composition changes, and provide swab kits. Households that continue to meet eligibility criteria (Table 2) may continue into the next respiratory season. Households will receive \$50 on enrollment and \$25 at this re-enrollment visit; this will aid with enrollment and retention. Participants will also receive compensation for reporting and returning self-swabs as outlined below. If a household no longer meets eligibility criteria during a season or if are lost to follow-up, we will replace households in the same season if there are ≥2 months left in the influenza season or the next year if there are <2months left. Households that leave the study will be replaced using the same procedures as for the baseline sample using 1:1 randomization. Based on previous studies, we expect 10-20% of households to be replaced yearly.^{18,29,67}

TEXT MESSAGE SURVEILLANCE FOR ILI/ARI

Both arms (surveillance + education vs. surveillance-only) will receive text messages to perform surveillance of household members for ILI/ARI. The surveillance period will run November through March each year. We have chosen that period since for the past 9 years (with the exception of the 2009 influenza A H1N1 pandemic) the earliest onset of influenza in these communities has been in November and we have seen the vast majority of influenza cases by March.^{18,68} If there are unusual influenza patterns, we will be able to start sample collection earlier or end it later. During the surveillance period, each household reporter in all households will automatically receive text messages three-times a week from the text messaging system (a.k.a. *research staff-generated messages*) asking if any household member has symptoms included in the study case definitions for ILI/ARI and asked to respond whether or not anyone is ill (Figure 3). Households will be texted on a Monday, Wednesday and Friday schedule to optimize days between reporting. We have chosen this schedule so that intervention can start within 36 hours of onset. Messages will be sent in English or Spanish based on the

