Laboratory Confirmation of Respiratory Pathogens. When a mailed swab sample is received, it will be logged into a database and placed in a designated refrigerator (2-8°C) prior to processing. Samples that cannot be fully processed within 48 hours will be aliquoted frozen at minus 80°C. Samples will be analyzed using the FilmArray instrument Respiratory Panel developed by BioFire Diagnostics,⁷⁵⁻⁷⁷ which has FDA 510(k) clearance as an *in vitro* diagnostic device for nasal swab specimens, and is the testing system we use in our current MoSAIC study. The Respiratory Panel applies multiplex reverse-transcriptase polymerase chain reaction (RT-PCR) to identify 20 respiratory pathogens using a variety of gene targets for specific pathogens⁷⁵(Appendix). Detected pathogens include Influenza A, Influenza A subtype H1, Influenza A subtype H3, Influenza A subtype H1 2009, Influenza B, adenovirus, 4 subtypes of coronavirus and 4 subtypes of parainfluenza, human metapneumovirus, respiratory syncytial virus, rhinovirus/enterovirus, *Mycoplasma pneumoniae*, *Chlamydophilia pneumoniae* and *Bordetella pertussis*. The sensitivity of FilmArray Respiratory Panel ranges from 87-100% and specificity from 89-100%. Previous studies have shown that the rates of detection of respiratory viruses by RT-PCR can be up to 2-fold higher than by conventional viral culture.⁷⁸ Testing will be performed within a research laboratory at Columbia University Medical Center and the technologist, [name], is the chief technologist on our MoSAIC study which also uses the FilmArray system. She will be supervised by [name]. [name] will provide expertise in viral diagnostic testing. Quality control will be performed for all new lots and shipments using validation panels as per the manufacturer's recommendations for research studies. The technical failure rate has been estimated to be 2-4%;^{76,77} but in our current study, the failure rate has been only 1.3%. In the event of technical failure, there is adequate residual viral transport media volume to perform a second test. For households with an influenza positive index case, if both d3 and d5 samples in a household member are negative, the d5 sample will be re-tested. The residual viral culture media containing the sample and swab will be stored in a minus 80°C freezer. Results will not be shared with participants and [name] and project coordinator will be blinded to study arm. However, if a household's index case has a negative result two episodes in a row, the study team may further assess the episodes and review with the household how to take the swab as well as the importance that symptoms be met.

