All analyses will be based on randomized arm assignment (intention-to-treat). An ill person will be considered an ILI/ARI index case for a household if, at the onset of illness, no one else in the household had been symptomatic within the previous 5 days.²⁹ Non-index household members will be defined as secondary cases if they are confirmed by RT-PCR as influenza-positive on day 3 or day 5 swab (symptomatic or asymptomatic).¹⁶ Five days was selected based on our previous studies and the influenza incubation period.²⁹ The secondary attack rate will be defined as the number of secondary cases of laboratory-confirmed influenza (both symptomatic and asymptomatic) divided by the number of household members minus one (the index case). Secondary attack rates will be compared between the arms - surveillance plus education vs. surveillance-only - using chi square tests and a generalized linear mixed model (logistic regression for binary response, mixed model for clustering within a household). We will assess other co-variates in the models including for the index patient and household contacts: age, sex, vaccination status including vaccine type, antiviral use (treatment or prophylaxis), previous illness episodes reported for the household, influenza season and years in study.

Secondarily, we will assess the intervention's impact on additional outcomes using the same analyses as above: defining secondary cases based on (1) ILI-criteria (fever, cough, headache, sore throat, or myalgia) within 5 days of illness of index case; (2) ARI criteria (≥ 2 of a) rhinorrhea/nasal congestion; b) sore throat; c) cough; d) fever/feverishness; e) myalgia); (3) any laboratory-confirmed pathogen that is the same as the index case including non-influenza pathogens. An additional set of secondary outcome measures will be to assess the secondary attack rate at the household (cluster) level defined as the percentage of households with at least one secondary case as defined in the analyses above.

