We will use Pearson chi square to assess relationship between text message response rates and community, reporter's race/ethnicity, insurance and education. This will be defined as number of responses received per message sent. If more than one variable is significantly related to reporting rates ($p<0.1$), we will develop multivariable logistic models to assess this relationship. We will also assess response rates by arm.

SAMPLE SIZE AND POWER

We have based our sample size on the primary outcome. With 200 households per arm and an average of 3.8 persons/household, we will have 88% power to detect a decrease in secondary attack rates of laboratory-confirmed influenza from 12% (surveillance-only) to 5% (surveillance + education), based on type I error of 5% and an intracluster correlation coefficient of 0.29. The intracluster correlation, expected transmission rates for the surveillance-only arm, and effect size are derived from the paper by Cowling *et al.*, reporting a reduction from 12% to 5% between the hand hygiene and usual care arms in SAR when a non-text message based behavioral intervention was started at ≤ 36 hours of illness onset in the index case using laboratory-confirmed influenza as an outcome.¹⁶ In the MoSAIC study, secondary attack rates for laboratory-confirmed influenza have been 16.6% therefore an expected rate of 12% in the surveillance-only arm is conservative. We will also be powered for our secondary outcome; we will have 91% power to detect a decrease in symptomatic ILI/ARI from 23% to 11%.¹⁶ If we lose 80 households (20%) per season, we will still have at least 80% power to detect the decreases in both the primary and secondary outcome as above, even without household replacement.

POTENTIAL CHALLENGES AND SOLUTIONS Table 3

Challenge	Solution
1. Recruitment and retention	In our previous community studies retention was excellent. In our MoSAIC study, 75.9% of households recruited in year 1 were still in the study in year 3.
2. Non-representative sample	Since eligibility criteria include ≥ 3 members and ≥ 1 child, the sample will not be fully representative of the communities. However, the benefits of these inclusion criteria include higher likelihood of infection and transmission.
3. Reporting bias	3x/a week texting will decrease recall bias. We have shown under- and over-reporting to be low and confirmed the validity of household symptom self-reports.

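### The 88% power assumes one influenza-positive index episode per household and the full within-36-hours effect in every episode; the plan states neither, and its attack-rate denominator does not match the 12% v 5% used

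*Combined protocol and SAP*

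**What the plan says.** **Sample Size and Power.** "With 200 households per arm and an average of 3.8 persons/household, we will have 88% power to detect a decrease in secondary attack rates" from 12% to 5%, with type I error 5% and an intracluster correlation (ICC) of 0.29. The rates and the ICC come from a published household trial, from the comparison in which the intervention began within 36 hours of index onset. The section calls 12% conservative because the team's earlier surveillance study saw 16.6%. It adds 91% power for the symptomatic outcome (23% v 11%), and at least 80% power if 80 households are lost per season without replacement.

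**Statistical Plan.** "An ill person will be considered an ILI/ARI index case for a household if, at the onset of illness", nobody else in the household had been symptomatic in the previous 5 days. The secondary attack rate (SAR) is the number of confirmed secondary influenza cases "divided by the number of household members minus one (the index case"). Analysis is by randomised arm.

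**Laboratory Confirmation of Respiratory Pathogens.** A re-test rule singles out a narrower group: "For households with an influenza positive index case, if both d3 and d5 samples in a household member are negative". It is a laboratory rule and does not define an analysis set.

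**Timing.** Specific Aims says "non-pharmaceutical interventions are effective only if started within 36 hours of index case symptom onset". Significance says the cited trial showed an effect "only when initiated within 36 hours of symptom onset in the index case". Text Message Surveillance sets Monday, Wednesday and Friday prompts and says "We have chosen this schedule so that intervention can start within 36 hours of onset". Household-generated messages also trigger staff contact. The visible text gives no expected share reached in time.

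**The concern.** Households are randomised at enrolment, before anyone is ill. A household contributes to a 12% v 5% comparison only if someone in it later becomes an influenza-positive index case, and it contributes the full effect only if the messages start in time. The power paragraph treats both as certain. It also uses rates that belong to a different denominator from the one in the Statistical Plan.

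This paragraph is the only justification of the sample size. By the plan's own premise late starts have no effect, and under intention-to-treat they stay in the comparison and dilute it. A reader cannot tell from the visible plan how much of the 88% survives.

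**Working it through.** **Method.** Two-proportion normal approximation, pooled null variance, two-sided 5% (sidedness is not stated), with n the effective number of contacts per arm:

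power = Φ{ [ |p1−p2|√n − 1.96√(2p̄(1−p̄)) ] / √[p1(1−p1)+p2(1−p2)] }, where n = episodes × 2.8 / DE.

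**Reproducing 88%.** Contacts per arm: 200 × (3.8 − 1) = 560. DE = 1 + 2.8 × 0.29 = 1.812, so n = 309 and power is **87.9%**. This mixes 2.8 contacts with a design effect based on 3.8 persons. Using 2.8 throughout, DE = 1 + 1.8 × 0.29 = 1.522, n = 368 and power is **92.7%**. The mix is conservative but unstated. Below, the first figure uses 1.812 and the bracketed figure 1.522.

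**Denominator.** Preliminary Studies 3.1: 59.5% of samples were positive for a pathogen, and 21.4% of the November–March positives were influenza. 0.595 × 0.214 = 0.127 (assuming 59.5% also applies in November–March). If secondary influenza follows only an influenza-positive index, the rates over all ILI/ARI episodes are 12% × 0.127 = 1.5% and 5% × 0.127 = 0.6%.

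**Timing.** The gaps between prompts are 48, 48 and 72 hours, all longer than 36. With onsets uniform over the week, instant reply and no other reporting route, the timely share is 3 × 36 / 168 = 64%. Household-generated reports raise this. Non-response (77.1% of texts were answered in the earlier study) and the confirmation call lower it. With no effect in late starts, education SAR = control × (1 − share × 7/12). At 200 episodes per arm:

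| Timely share | Control 12% | Control 16.6% |
|---|---|---|
| 100% | 88% (93%) | 96% (98%) |
| 85% | 73% (81%) | 87% (92%) |
| 64% | 47% (54%) | 62% (70%) |

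Holding 80% power needs about 91% (85%) timely at a 12% control rate, or 78% (72%) at 16.6%.

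**Episodes, full effect.**

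| Influenza-index episodes per arm | Control 12% | Control 16.6% |
|---|---|---|
| 100 | 60% (67%) | 76% (82%) |
| 150 | 77% (84%) | 90% (94%) |
| 200 | 88% (93%) | 96% (98%) |
| 250 | 94% (97%) | 99% (>99%) |

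The plan's own figures allow only a rough guess at the number per arm, taking three seasons:
- From 5–15 ill households per reporting day and about 64.7 reporting days a season (151 × 3/7): (5 to 15) × 64.7 × 3 × 0.127 / 2 = 62 to 185.
- From 78 confirmed cases in 509 households of an earlier trial, taken as one season's yield: 78/509 × 200 × 3 = 92.
- From that trial's 669 ILI cases at 33.3% swab positivity: 669 × 0.333/509 × 200 × 3 = 263.

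These straddle 200.

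**Secondary outcome.** 23% v 11% with ICC 0.29 gives 98% at DE 1.812. To obtain 91% by the same method needs an ICC of about 0.59.

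**Attrition.** A loss of 80 is 40 per arm. Over three equal seasons:
- Losses after each season: (200 + 160 + 120)/3 = 160 per arm, 79.9% (86%).
- Mid-season losses: (180 + 140 + 100)/3 = 140, 74% (81%).
- Losses before each season: (160 + 120 + 80)/3 = 120, 68% (75%).

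**The case against.** The best defence is that the 88% already carries two cushions: a conservative design effect, and a 12% control rate where the team has seen 16.6%. This stands in part. At 16.6%, 150 episodes with full effect still give 90% (94%), and 85% timely gives 87% (92%). So it would be wrong to infer that 88% is reachable only when both the number of episodes and the timely share are favourable.

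Other stronger readings also fail on the documents:
- **That true power is 47%, or lower.** The 64% share leaves out household-generated reports, and part of the text on reporting is not visible. Scaling 64% down by 77.1% would treat each unanswered text as a missed illness, but that figure is per message.
- **That there will be too few influenza episodes.** The rough counts straddle 200. The lowest treats a staff-workload figure as new episodes, and the 92 rests on a trial that swabbed only some of its illnesses, whereas this one swabs anyone meeting ARI or ILI criteria.
- **That the secondary 91% is an error.** No ICC is stated for that outcome. With 0.29 the figure would be higher, so 91% is conservative and not shown to be wrong.
- **That attrition cuts power to 68%.** That is the worst case. Households contribute episodes before they leave, and the plan does replace them.

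The denominator may be only a wording gap, since the re-test rule points to influenza-positive index cases. Nor does the wider denominator by itself cost much power, because contacts increase as the rates fall. But the primary endpoint as written is still not the one whose rates were used.

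**Conclusion.** The concern holds as one of unstated assumptions and a mismatched endpoint definition. The arithmetic of the 88% is sound for its inputs. What the plan lacks is a link from those inputs to its own endpoint rule, prompt schedule and intention-to-treat analysis: an average of one influenza-positive index episode per household, full effect in all of them, and a denominator to which 12% v 5% applies.

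The timing assumption matters most. At 200 episodes and a 12% control rate, moving from all timely to 85% timely costs about 15 points (12 with the consistent design effect). The results assume no effect after 36 hours (the plan's own premise), the same relative reduction at 16.6%, and repeat episodes in a household treated as independent clusters. A reader might conclude that the trial is underpowered; the documents do not show that, because the visible text gives neither the expected episodes nor the expected timely share.

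**What to change.** 1. In the Statistical Plan, restrict the primary SAR to contacts of influenza-positive index cases, so that it matches the rates used for power, and say how repeat episodes in a household count.
2. In Sample Size and Power, replace the single 88% with power over a range of influenza-index episodes per arm and shares reached within 36 hours, at control rates of 12% and 16.6%. Give the expected value of each, including the contribution of household-generated reports, and state the cluster size in the design effect.
3. State the ICC behind the secondary 91%.
4. Clarify the loss of 80 households per season: how many seasons it covers, when losses are assumed to occur, and the average number of households per arm that results.

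This is wording only, with no extra households and no change to the primary test; index cases are already swabbed. The cost is that the stated power becomes a range that may look less favourable than 88%.
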